7.4 Demographic and Other Baseline Characteristics

Analysis set:

Safety analysis set

Analysis variable(s):

Age (years) [6, 7, 8, 9, 10, 11, 12, 13, 14, 15]

Gender [Male, Female]

Height (cm) at Week 0 [Min \le - \le 99, 100 \le - \le 109, 110 \le - \le 119, 120 \le - \le 129, 130 \le - \le 139, 140 \le - \le 149, 150 \le - \le 159, 160 \le - \le 169, 170 \le - \le 179, 180 \le - \le Max]

Weight (kg) at Week 0 [Min \le - \le 19.9, 20.0 \le - \le 29.9, 30.0 \le - \le 39.9, 40.0 \le - \le 49.9, 50.0 \le - \le 59.9, 60.0 \le - \le 69.9, 70.0 \le - \le 79.9, 80.0 \le - \le Max]

 $[Min \le - \le 49.9, 50.0 \le - \le Max]$

BMI (kg/m²) at Week 0 [Min≤ - ≤14.9, 15.0≤ - ≤17.9, 18.0≤ - ≤20.9, 21.0≤ - ≤23.9, 24.0≤ - ≤26.9, 27.0≤ - ≤Max]

Disease duration (years) $[Min \le - \le 0.9, 1.0 \le - \le 1.9, 2.0 \le - \le 2.9, 3.0 \le - \le 3.9, 4.0 \le - \le Max]$

Type of hypertension [Essential hypertension, Secondary hypertension]

Drug induced hypertension [Yes, No]

Disease induced hypertension [Yes, No]

History of kidney transplantation [Yes, No]

Antihypertensive drugs prior to Run-in Period [Yes, No]

ACE inhibitors [Yes, No]

ARB [Yes, No]

DRI [Yes, No]

CCB [Yes, No]

Diuretics [Yes, No]

Alpha-blockers [Yes, No]

Beta-blockers [Yes, No]

Other [Yes, No]

RAS inhibitors (ACE inhibitors, ARB, and DRI) prior to Run-in Period [Yes, No]

Antihypertensive drugs at the start of Treatment Period I [Yes, No]

CCB [Yes, No]

Diuretics [Yes, No]

Alpha-blockers [Yes, No]
Beta-blockers [Yes, No]
Other [Yes, No]

Office sitting blood pressure (systolic) (mmHg) at Week 0 [Min \leq - \leq 109, 110 \leq - \leq 119, 120 \leq - \leq 129, 130 \leq - \leq 139, 140 \leq - \leq Max]

Office sitting blood pressure (diastolic) (mmHg) at Week 0 [Min \leq - \leq 69, 70 \leq - \leq 79, 80 \leq - \leq 89, 90 \leq - \leq 99, 100 \leq - \leq Max]

eGFR (mL/min/1.73 m²) [Min \le - \le 29, 30 \le - \le 59, 60 \le - \le 89, 90 \le - \le Max]

Analytical method(s):

The following analysis will be performed for the above analysis variables by weight group ($< 50 \text{ kg}, \ge 50 \text{ kg}$) and in the combined weight groups.

(1) Frequency distributions for categorical variables and summary statistics for continuous variables

7.5 Medical History and Concurrent Medical Conditions

Analysis set:

Safety analysis set

Analysis variable(s):

Underlying diseases of secondary hypertension

Medical history (other than the underlying disease of secondary hypertension)

Concurrent medical conditions (other than the underlying disease of secondary hypertension)

Analytical method(s):

The following analysis will be performed for the above analysis variables by weight group ($< 50 \text{ kg}, \ge 50 \text{ kg}$) and in the combined weight groups.

Analysis variables will be coded using MedDRA and will be summarized based on SOCs and PTs. SOCs will be sorted alphabetically and PTs will be sorted in decreasing frequency.

- (1) Frequency distributions for underlying diseases of secondary hypertension by SOC and PT
- (2) Frequency distributions for medical history by SOC and PT
- (3) Frequency distributions for concurrent medical conditions by SOC and PT

The frequency distributions will be provided according to the rules below:

[Number of subjects]

A subject with multiple occurrences of medical history or concurrent medical condition within a SOC will be counted only once in that SOC. A subject with multiple occurrences of medical history or concurrent medical condition within a PT will be counted only once in that PT.

7.6 Medication History and Concomitant Medications

Analysis set:

Safety analysis set

Analysis variable(s):

Medication history

Concomitant medications (antihypertensive drugs)

Concomitant medications (other than antihypertensive drugs)

Analytical method(s):

The following analysis will be performed for the above analysis variables by weight group ($< 50 \text{ kg}, \ge 50 \text{ kg}$) and in the combined weight groups.

Analysis variables will be coded using the WHO Drug and will be summarized based on Preferred Name, which will be sorted in decreasing frequency. A subject who has been administered several medications with the same Preferred Name will be counted only once for that Preferred Name.

- (1) Frequency distributions for medication history
- (2) Frequency distributions for concomitant medications (antihypertensive drugs) that stopped prior to the study drug administration for the Treatment Period
- (3) Frequency distributions for concomitant medications (antihypertensive drugs) that started prior to the study drug administration for the Treatment Period and were ongoing during the Treatment Period
- (4) Frequency distributions for concomitant medications (antihypertensive drugs) that started after the study drug administration for the Treatment Period
- (5) Frequency distributions for concomitant medications that started prior to the study drug administration for the Treatment Period and were ongoing during the Treatment Period and concomitant medications (other than antihypertensive drugs) that started after the study drug administration for the Treatment Period

7.7 Study Drug Exposure and Compliance

7.7.1 Study Drug Exposure and Compliance

Analysis set:

Safety analysis set

Analysis variable(s):

Duration of exposure to study drug for the Treatment Period (days) $[1 \le - \le 84, 85 \le - \le 168, 169 \le - \le 252, 253 \le - \le 336, 337 \le - \le 420, 421 \le - \le Max]$

Study drug compliance rate for the Treatment Period (%) [Min \leq - \leq 69.9, 70.0 \leq - \leq 79.9, 80.0 \leq - \leq 89.9, 90.0 \leq - \leq Max]

Analytical method(s):

The following analysis will be performed for the above analysis variables by weight group ($< 50 \text{ kg}, \ge 50 \text{ kg}$) and in the combined weight groups.

(1) Frequency distributions for categorical variables and summary statistics for continuous variables

7.7.2 Dose Escalation

Analysis set:

Safety analysis set

Analysis variable(s):

Dose dispensed at each visit [2.5 mg, 5 mg, 10 mg, 20 mg, 40 mg]

Visit:

Weeks 0, 2, 4, 6, 8, 12, 16, 20, 24, 32, 40, and at the End of Treatment Period

Analytical method(s):

The following analysis will be performed for the above analysis variables by weight group ($< 50 \text{ kg}, \ge 50 \text{ kg}$) and in the combined weight groups.

For the dose dispensed at each visit, the dose dispensed on the day of first study drug administration for the Treatment Period will be used for Week 0 and the dose dispensed on the day before the visit day will be used except for Week 0. If dose on the visit day is missing, the last dose dispensed by the scheduled study day (Days 1, 15, 29, 43, 57, 85, 113, 141, 169, 225, and 281 for Weeks 0, 2, 4, 6, 8, 12, 16, 20, 24, 32, and 40, respectively [the day of the first study drug administration for the Treatment Period to be defined as Day 1]) will be used until the day of study drug discontinuation. After the day of study drug discontinuation, the dose dispensed on that visit will be handled as missing and excluded from summaries.

The dose dispensed at the End of the Treatment Period will be the last dose dispensed for each subject.

(1) Frequency distributions

7.8 Efficacy Analysis

7.8.1 Primary Efficacy Endpoint(s)

The safety endpoints are the primary endpoints in this study.

7.8.2 **Secondary Efficacy Endpoint(s)**

Analysis set:

Full analysis set

Analysis variable(s):

Office trough sitting diastolic blood pressure

Office trough sitting systolic blood pressure

Proportion of subjects who achieved the target blood pressure

Visit:

Weeks 0, 2, 4, 8, 12, 16 (postdose), 20, 24, 32, 40, 52, 54 (Follow-up Period), at the End of Treatment Period I, and at the End of Treatment Period

Analytical method(s):

The following analyses (1) and (2) will be performed for office trough sitting diastolic and systolic blood pressures by weight group ($< 50 \text{ kg}, \ge 50 \text{ kg}$) and in the combined weight groups.

The following analysis (3) will be performed for the proportion of subjects who achieved the target blood pressure by weight group ($< 50 \text{ kg}, \ge 50 \text{ kg}$) and in the combined weight groups.

The measurement at Week 16 (postdose) will be performed after the study drug administration, while the measurement at other visits than Week 16 (postdose) will be performed before the study drug administration.

- (1) Summary statistics and 2-sided 95% confidence intervals of means at each visit will be calculated.
- (2) Summary statistics and 2-sided 95% confidence intervals of means will be calculated for changes (each visit after Week 2 Week 0) at each visit. For the population in the combined weight groups, a one-sample t-test will be applied for reference.
- (3) Frequency distributions will be provided at each visit and the 2-sided 95% confidence interval of the proportion will be calculated.

7.8.3 Additional Efficacy Endpoint(s)

Analysis set:

Full analysis set

Analysis variable(s):

Home sitting diastolic blood pressure

Home sitting systolic blood pressure

Visit:

Weeks 0 (predose), 0 (postdose), 2, 4, 8, 12, and at the End of Treatment Period I

Analytical method(s):

The following analyses will be performed for home sitting diastolic and systolic blood pressures by weight group ($< 50 \text{ kg}, \ge 50 \text{ kg}$) and in the combined weight groups.

- (1) Summary statistics and 2-sided 95% confidence intervals of means at each visit will be calculated.
- (2) Summary statistics and 2-sided 95% confidence intervals of means will be calculated for changes (each visit after Week 0 (postdose) Week 0 (predose) at each visit. For the population in the combined weight groups, a one-sample t-test will be applied for reference.

7.8.4 Statistical/Analytical Issues

7.8.4.1 Adjustments for Covariates

Not applicable in this study.

7.8.4.2 Handling of Dropouts or Missing Data

Missing test results will be excluded from statistical analyses and estimations for that item. Plasma concentrations and clinical laboratory data below the lower limit of quantification will be handled as 0. Clinical laboratory data above the upper limit of quantification will be handled as the upper limit of quantification.

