5. Withdrawal by subject. The subject wishes to withdraw from the study. The reason for withdrawal, if provided, should be recorded in the eCRF.

Note: All attempts should be made to determine the underlying reason for the withdrawal and, where possible, the primary underlying reason should be recorded (i.e., withdrawal due to an AE).

6. Withdrawal by parent or guardian. The subject's parent or the subject's legal guardian wishes to withdraw the subject from the study. The reason for withdrawal, if provided, should be recorded in the eCRF.

Note: All attempts should be made to determine the underlying reason for the withdrawal and, where possible, the primary underlying reason should be recorded (i.e., withdrawal due to an AE).

7. Study terminated by sponsor. The sponsor terminates the study.

8. Pregnancy. The subject is found to be pregnant.

Note: If the subject is found to be pregnant, the subject must be withdrawn immediately. The procedure is described in Section 9.1.11.

9. Lack of efficacy. The investigator or subinvestigator has determined that the subject is not benefiting from study treatment; and, continued participation would pose an unacceptable risk to the subject. For example, discontinuation should be considered in the following case; on consecutive visits, an office sitting systolic blood pressure is persistently higher by at least 15 mmHg and/or an office sitting diastolic blood pressure is persistently higher by at least 10 mmHg than the 99 percentiles of the reference blood pressure values of children by gender and age in Table 5.a, or, subjective symptoms or findings deemed associated with poorly controlled blood pressure do not improve with titration of TAK-536 during the Treatment Period I or with the addition of any other antihypertensive drugs other than RAS inhibitors during the Treatment Period II.

10. Other.

Note: The specific reasons should be recorded in the "specify" field of the eCRF.

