13.1.3 Efficacy Analysis

(1) Secondary endpoints and analytical methods

[Secondary endpoints]

Office trough sitting systolic and diastolic blood pressure, proportion of subjects who achieve the target blood pressure

[Analytical methods]

The analyses discussed below will be conducted with the FAS.

Summary statistics (number of subjects, mean, standard deviation, maximum, minimum, and quartiles; hereinafter the same) and 2-sided 95% confidence intervals for mean values will be calculated for the office trough sitting systolic and diastolic blood pressure at each time point (including the end of the Treatment Period I and the end of the Treatment Period II; hereinafter the same).

Summary statistics and 2-sided 95% confidence intervals for mean values will be calculated referring to a 1-sample t-test for the change of office trough sitting systolic and diastolic blood pressure from the end of the Run-in Period (Week 0) to each time point during the Treatment Period.

The proportion of subjects who achieve the target blood pressure at each time point during the Treatment Period will be summarized.

(2) Data conversion methods and handling of missing data

Details of data conversion methods and handling of missing data will be defined in the Handling Rule for Analysis and SAP.

(3) Significant level and confidence coefficient

Significant level: 5% (2-sided test)

Confidence coefficient: 95% (2-sided estimates)

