6.0 DETERMINATION OF SAMPLE SIZE

Total of 50 subjects (who enter the Treatment Period).

[Sample Size Justification]

A total of 50 subjects to enter the Treatment Period was set in consideration of feasibility.

Assuming a mean change of trough sitting diastolic blood pressure from the end of the Run-in Period (Week 0) to the end of Treatment Period I of -6.5 mmHg and an SD of 10.5 mmHg, and a mean change of trough sitting systolic blood pressure from the end of the Run-in Period (Week 0) to the end of Treatment Period I of -9.5 mmHg and an SD of 15.5 mmHg, the planned 50 subjects will provide at least 90% power by a 1-sample t-test at a 0.05 significance level (2-sided).

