- Achievement of target blood pressure on each measuring day: Subjects are determined to have achieved their target blood pressures if their blood pressures are the < 95th percentile (both diastolic and systolic) shown in Table 5.a Reference Blood Pressure Values of Children by Gender and Age for essential hypertension or < 90th percentile (both diastolic and systolic) shown in Table 5.a Reference Blood Pressure Values of Children by Gender and Age for secondary hypertension. If either systolic or diastolic blood pressure is missing, it will be handled as missing data. The age at the time of informed consent will be used.

- Disease duration (years): (Date of informed consent [year and month] Time of onset [or diagnosis] of underlying disease [year and month]) / 12 (rounded to 1 decimal place) For the date of informed consent, only the year and month will be used. If the year of onset (or diagnosis) of underlying disease is unknown, it will be classified as "Unknown." If only the month of onset (or diagnosis) of underlying disease is unknown, the disease duration will be calculated with the month of onset (or diagnosis) of underlying disease as January.
- QTcF interval: Fridericia's formula (QT interval / [RR interval^{0.33}])
- CV (%): Standard deviation / mean × 100

7.1.2 **Definition of Study Days**

- Study Day: The day before the first study drug administration for the Treatment Period will be defined as Day -1 and the day of the first study drug administration for the Treatment Period will be defined as Day 1.
- Follow-up Day: The day after the last study drug administration for the Treatment Period will be defined as Follow-up Day 1.

7.1.3 **Definition of Study Visit Windows**

For each test, observation, and endpoint except for home blood pressure, all evaluable data (i.e., non-missing data) will be handled according to the following rules.

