For each visit other than the End of Treatment Period I and the End of Treatment Period, the evaluable data within the acceptable time window will be used. If more than one evaluable datum lies within the same acceptable time window, the data whose test/observation/evaluation time point is closest to the scheduled time point will be used. If there are two data equidistant to the scheduled time point, the data obtained later will be used. The temporal distance from the scheduled time point will be determined based on the Study Day and the time interval between the latest study drug administration and the blood sample collection.

For the End of Treatment Period I and the End of the Treatment Period, the evaluable data within the acceptable time window with the largest Study Day will be used.

Table 7.a Visit Window of Office Sitting Blood Pressure and Pulse Rate

Visit	Cahadulad Study Day	Acceptable Time Window	
Visit	Scheduled Study Day	Study Day	Follow-up Day
At the End of Run-in Period (Week 0)	Study Day: 1	-28 to 1	
Week 2	Study Day: 15	2 to 22	< 4
Week 4	Study Day: 29	23 to 43	< 4
Week 8	Study Day: 57	44 to 71	< 4
Week 12	Study Day: 85	72 to 99	< 4
Week 16 (postdose)	Study Day: 113	100 to 127	< 4
Week 20	Study Day: 141	128 to 155	< 4
Week 24	Study Day: 169	156 to 183	< 4
Week 32	Study Day: 225	184 to 253	< 4
Week 40	Study Day: 281	254 to 323	< 4
Week 52	Study Day: 365	324 to 372	< 4
Week 54 (Follow-up Period)	Study Day: 379	373 to 386	> 0
At the End of Treatment Period I*1		2 to 99	< 4
At the End of Treatment Period*2		2 ≤	< 4

^{*1} Data obtained after the earliest day of addition or dose change of antihypertensive drugs other than RAS inhibitors during the Treatment Period will not be used for summaries. Not applicable for office sitting pulse rate.
*2 The condition of *1 will not apply to this handling. Not applicable for office sitting pulse rate.

Table 7.b Visit Window of Clinical Laboratory Test Items

Visit	Scheduled Study Day	Acceptable Time Window	
V ISIL	Scheduled Study Day	Study Day	Follow-up Day
At the End of Run-in Period (Week 0)	Study Day: 1	-28 to 1	
Week 2	Study Day: 15	2 to 22	< 15
Week 4	Study Day: 29	23 to 43	< 15
Week 8	Study Day: 57	44 to 71	< 15
Week 12	Study Day: 85	72 to 99	< 15
Week 16 (postdose)	Study Day: 113	100 to 141	< 15
Week 24	Study Day: 169	142 to 225	< 15
Week 40	Study Day: 281	226 to 323	< 15
Week 52	Study Day: 365	324 to 379	< 15

Table 7.c Visit Window of Office Standing Blood Pressure and Pulse Rate

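### The long-term proportion at target drops children who stopped, and the SAP's end-of-study row is a last reading from Day 2 on, not the end of Treatment Period II that the protocol names

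*SAP*

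**What the plan says.** **Denominator.** The full analysis set (FAS) is every child dosed in the Treatment Period (SAP 7.2). SAP 7.8.2(3) gives a frequency distribution and 95% confidence interval for the proportion at target at each visit, including Weeks 20, 24, 32, 40 and 52, and at two end rows. SAP 7.8.4.2 states: "Missing test results will be excluded from statistical analyses and estimations for that item". For target achievement, SAP 7.1.1 adds: "If either systolic or diastolic blood pressure is missing, it will be handled as missing data". No analysis counts a child who has stopped as not at target.

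**End of study.** Protocol 13.1.3 lists its time points as "including the end of the Treatment Period I and the end of the Treatment Period II; hereinafter the same". It does not define the second, and it leaves missing-data detail to the SAP and to a Handling Rule for Analysis that is not among the documents reviewed. SAP Table 7.a has a row for the end of Treatment Period I (Days 2 to 99) and one for the end of the whole Treatment Period (Day 2 on, Follow-up Day < 4), but none for Treatment Period II. For both end rows SAP 7.1.3 says "the evaluable data within the acceptable time window with the largest Study Day will be used". SAP 7.13 declares one change only, on home blood pressure.

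**Exits.** Protocol 7.5 lists, among other reasons, an adverse event, and lack of efficacy where the investigator "has determined that the subject is not benefiting from study treatment". Protocol 9.3.5 asks for an office sitting reading within 3 days of early termination, which fits Follow-up Day < 4.

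**The concern.** A 52-week study is read for how many treated children are still on the drug and controlled late on. No planned row gives that.

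- The Week 52 row uses readings on Days 324 to 372. A child whose last usable reading is earlier is in neither numerator nor denominator.
- The end-of-treatment row keeps leavers but mixes exposures: an exit reading at Week 4 counts beside a reading at Week 52. A child who stopped for an adverse event counts as a success if the last reading was below target.
- That row does not exclude the Week 16 reading, which is taken after dosing (Days 100 to 127). If it is a child's last usable reading, a non-trough value enters a trough endpoint.

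The two rows answer different questions, and neither corrects the other. Protocol 6.2 says the office trough pressures were chosen partly to show persistence of effect, so the late figures will be used.

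**Working it through.** **The plan's own figure.** SAP 6.0 claims at least 90% power with 50 children at two-sided 5%, for changes at the end of Treatment Period I. It assumes a diastolic fall of "6.5 mmHg and an SD of 10.5 mmHg" and a systolic fall of 9.5 mmHg with SD 15.5. The noncentrality parameters are 6.5/10.5 × √50 = 4.38 and 9.5/15.5 × √50 = 4.33. Exact one-sample t-test power is 99.0% and 98.9%, so the claim is met. Each test needs 30 children for 90%, so up to 20 of the 50 could be missing. The point below does not touch this statement.

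**Observed-case against all treated children.** Inputs: N = 50 (SAP 6.0); L = children who left before the visit; x = children at target at the visit. L and the rate are assumptions, because the documents give neither. No missed visits among children still on drug are assumed.

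- Observed-case proportion: p = x/(50 − L).
- Share of all treated children on drug and at target: x/50.
- Gap: x/(50 − L) − x/50 = p × (L/50).

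With p = 60% (Clopper-Pearson 95% intervals):

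| Left (L) | Observed-case | All treated | Gap |
|---|---|---|---|
| 5 | 27/45 = 60% (44.3 to 74.3) | 27/50 = 54% (39.3 to 68.2) | 6 points |
| 10 | 24/40 = 60% (43.3 to 75.1) | 24/50 = 48% (33.7 to 62.6) | 12 points |
| 15 | 21/35 = 60% (42.1 to 76.1) | 21/50 = 42% (28.2 to 56.8) | 18 points |

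At L = 10, a rate of 50% gives 20/40 against 20/50, a gap of 10 points. A rate of 70% gives 28/40 against 28/50, a gap of 14 points.

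**Observed-case against the last-reading row.** Let q be the share of leavers at target at their last reading, with every leaver having one. The last-reading proportion is (x + qL)/50, and observed-case minus last-reading is (L/50) × (p − q). With L = 10 and x = 24:

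- q = 0: 24/50 = 48%
- q = 0.4: 28/50 = 56%
- q = 0.6: 30/50 = 60%
- q = 1: 34/50 = 68%

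The observed-case 60% is therefore above, equal to or below the last-reading figure according to whether leavers were at target less often than, as often as, or more often than those who stayed.

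**Which children the end rows treat differently.** For a child with a usable trough reading on Day 100 or later, the current row and a row restricted to those days pick the same value, unless the last reading is the Week 16 post-dose one. Otherwise they differ only for children with no trough reading after Day 99. The current row includes those children; the restricted row would not.

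**The case against.** A reader might infer that the Week 52 proportion is biased in the drug's favour in general. The documents do not support that. Lack-of-efficacy exits push the observed-case figure up, but exits of children at target, for example for low pressure, push it down, and neither a dropout rate nor a mix of reasons is given. The efficacy exit is also narrow. The pressure example in Protocol 7.5 is persistent readings at least 15/10 mmHg above the 99th percentile. Children merely above target can be titrated or given added drugs in Treatment Period II, so most failures on this endpoint would stay in the denominators. A child withdrawn on that pressure example who has an exit reading counts as not at target in the end-of-treatment row. All of this stands.

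The 6, 12 and 18 points are an identity against one chosen quantity, with assumed inputs. The protocol endpoint is being at target, not being on drug and at target. Both are true, which is why the added line should be supplementary.

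A reader might also infer that the SAP broke a protocol definition, or that only one row keeps leavers. The protocol gave a name without a definition, and the end of Treatment Period I row keeps leavers too.

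It can be said that a reader could divide the Week 52 count by the FAS, since SAP 7.3.5 and 7.3.6 tabulate stopping. That is only partly so. The exposure bands in 7.3.6 (253 to 336 days, then 337 to 420) do not line up with a window opening on Day 324, missed visits are not separated from stopping at each visit, and no interval is planned for that proportion.

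Finally, a row starting at Day 100 itself omits children who left in Treatment Period I. That is correct, and the fix has to report their number.

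**Conclusion.** The point holds in a limited form. Visit-wise proportions at target are observed-case. The end-of-study row is a last reading from Day 2 on that can mix in short exposure and a post-dose value. The time point named in the protocol has no row, and SAP 7.13 does not mention it.

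The observed-case figure exceeds the share of all treated children on drug and at target whenever anyone has left and any remaining child is at target. The size is the rate among those remaining times the share who left: 6 to 18 points for an assumed 60% rate and 5 to 15 leavers of 50. Against any other quantity the direction is open.

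The endpoint is secondary and descriptive, the primary endpoints are safety, and the power statement is unaffected. The change is a cheap improvement in what the long-term tables can be read to say, not a correction to a test.

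**What to change.** 1. **SAP 7.8.2(3), pre-dose visits from Week 20 to Week 52.** Add a supplementary line on all FAS children. A child who stopped study drug before the visit counts as not at target; a missed visit while on drug stays missing. Show it beside the observed-case line, with its 95% confidence interval.
2. **SAP Table 7.a.** Add a row for the end of Treatment Period II: the last trough reading on Day 100 or later, Follow-up Day < 4, excluding the Week 16 post-dose reading. Report how many FAS children have no such reading.
3. **Existing end-of-treatment row.** Exclude the Week 16 post-dose reading here too, and keep the row as supplementary.
4. **SAP 7.13.** Declare both changes to the end rows.

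The cost is SAP wording and one or two extra table lines. No new data are needed. The downside is that a less favourable proportion appears beside the current one.
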